1.4 Dose Rationale and Risk/Benefits

The Avmacol[®] dosing regimen for the current study was designed to deliver a slightly higher concentration of SF as that administered in a previously reported clinical trial of SF for ASD [48]. In the randomized, placebo-controlled trial by Singh et. al [48], participants randomly assigned to the active treatment group received capsules containing SF-rich broccoli sprout extracts that provided approximately 50 µmol SF/cap. Dosing was weight-based as follows:

50 μ mol SF (1 cap) daily for weight < 100 100 μ mol SF (2 caps) daily for weight 101-199 lb. 150 μ mol SF (3 caps) daily for weight ≥ 200 lb.

Using this dosing schedule, participants receiving SF demonstrated significant improvement in social impairment as measured by change in Social Responsiveness Scale (SRS) total scores and significant improvement in related challenging behaviors as measured by the Aberrant Behavior Checklist (ABC) as compared with placebo over the course of the 16-week active treatment period. Between group differences were first observed by week 4 of treatment. These doses of SF were well-tolerated by participants and were not significantly associated with adverse events, change in blood pressure or heart rate, or change in routine laboratory values. Unexpectedly, SF treatment was associated with minor but significant weight gain, and 2 participants with a history of seizures had single, unprovoked seizures (one taking SF, one taking placebo).

The currently proposed clinical trial is designed to independently replicate the study by Singh and colleagues [48], to support or refute these findings. Avmacol® delivers SF in the form of its glucosinolate precursor, glucoraphanin (GR; derived by broccoli seed extract), and the active enzyme myrosinase (derived from broccoli sprouts), which hydrolyzes GR to SF upon ingestion. Bioavailability studies have demonstrated approximately 40-50% endogenous conversion of GR to SF upon ingestion of compounds containing GR enriched with myrosinase in healthy participants [47]. Each tablet of Avmacol®, formulated for use in clinical trials, contains approximately 15 mg (34.4 μ mol) of glucoraphanin. Assuming 45% endogenous conversion of GR to SF (which will vary somewhat from individual to individual), each tablet will therefore supply approximately 15.5 μ mol SF/tablet. The weight-based Avmacol®/ placebo dosing schedule for the current study is as follows:

3 tablets (approx. 46.5 μ mol SF) if <100 lb 5 tablets (approx. 77.5 μ mol SF) if 100-125 lb 6 tablets (approx. 93 μ mol SF) if 126-175 lb 7 tablets (approx. 108.5 μ mol SF) if 176-199 lb 8 tablets (approx. 124 μ mol SF) if \geq 200 lb

Based on previous studies of SF in human subjects, this dosing regimen is expected to be very well-tolerated with minimal to no adverse effects. This dosing regimen is also expected to deliver a slightly higher weight-based dose of SF than the trial conducted by Singh et al [48] after accounting for the 70% bioconversion rate (approximate) when purified SF is administered orally (i.e., an oral dose of 50 μ g SF derived from freeze-dried BSE is expected to provide 35 μ g SF following ingestion and bioconversion).

If a participant experiences significant adverse events that affect tolerability, may reasonably be related to taking the investigational product, and do not meet the protocol definition for a serious AE, the dose may be reduced by approximately 30% according to the following dose modification schedule:

Weight	Prescribed weight-	Prescribed #	70% of	Prescribed #
category	based dose of	of tablets	weight-based	tablets for
	glucoraphanin		dose (ie, 30%	reduced dose
			reduction)	(rounded to
				nearest 15 mg
				increment)*
<100 lb	45 mg	3	31.5 mg	2
100-125 lb	75 mg	5	52.5 mg	3
126-175 lb	90 mg	6	63 mg	4
176-199 lb	105 mg	7	73.5 mg	5
≥ 200 lb	120 mg	8	84 mg	6

*Rounded down if equidistant between two 15 mg dosing increments

If the dose is reduced during the course of the study, the participant will continue the lowered dose for the remainder of the study. If adverse events do not improve within 14 days of lowering the dose, the investigational product may be permanently discontinued at the discretion of the treating study physician, participant, and participant's guardian. If a participant exhibits extreme exacerbation of behavioral symptoms (such as self-injurious behavior or aggression) that do not improve substantially following a dose reduction and are determined "probably" or "definitely" related to taking the investigational product, the investigational product may be permanently discontinued sooner than 14 days post-reduction, and the DSMB will be notified. As individuals with ASD often have cyclical changes in behavior independent of medication effects, the study staff will rely on caregivers' experience with the participant to determine if any observed behavior changes are within the expected range for that individual. If the investigational product is stopped permanently, the participant and his caregiver will be asked to complete the remainder of the study visits, return any unused study drug, and repeat safety lab studies.

2 Study Objectives

Primary Objective:

The primary objective of this clinical trial is to determine if Avmacol[®] is superior to placebo for improving social communication impairment in adolescent and young adult men with moderate to severe autism spectrum disorder (ASD), as measured by change in Social Responsiveness Scale-2 (SRS-2) [100] total scores.

Secondary Objectives:

Secondary objectives include: (1) assessing the safety and tolerability of Avmacol[®] in subjects with ASD; and (2) characterizing the effects of Avmacol[®] on behavioral challenges commonly associated with ASD, including hyperactivity, irritability, repetitive behavior, and inappropriate speech.

Exploratory Objectives:

In a subset of 30 participants, exploratory objectives include: (1) Assessment of gut micobiota diversity and relative abundance of microbial species from fecal samples collected before and after 12 weeks of treatment with sulforaphane or placebo. (2) Explore the relationship between changes in microbiota composition and behavioral outcomes in young men treated with sulforaphane or placebo.

3 Study Design

3.1 General Design

We propose to conduct a Phase II, randomized, double-blind, placebo-controlled trial of Avmacol®, a rich source of sulforaphane, for the treatment of social impairment in individuals with ASD. Fifty-four male subjects with autism spectrum disorder (ASD) between ages 13 and 30 years old will be randomized in a 1:1 ratio, stratified by age category (13-18 and 19-30 years old), to receive either Avmacol® or identical placebo tablets. Participation will be limited to males to closely approximate the sample used in the SF for ASD clinical trial by Singh et al. [48] and to account for possible mechanistic differences in ASD between males and females (ASD is 4 times more common in males). Stratification by age will account for possible age-based differences in response to treatment (adolescence vs. adulthood) and allow for secondary analysis by age group (adolescent vs. adult).

The length of study participation from baseline to study termination for each individual subject is 16 weeks, including a 12-week active treatment phase (Avmacol® or placebo), followed by a 4-week blinded discontinuation phase. Participants will be monitored with clinic visits at regular intervals (baseline and weeks 4, 8, 12, and 16) for improvement in a well-characterized, caregiver-rated measure of social impairment (Social Responsiveness Scale-2 (SRS-2) [100], the primary outcome) as well as secondary measures of (1) repetitive behaviors associated with ASD (Repetitive Behavior Scale- Revised; RBSR) [102]; (2) challenging behaviors commonly associated with developmental disabilities (Aberrant Behavior Checklist; ABC) [103]; (3) clinician-rated functional severity (Clinical Global Impression Scale- Severity; CGI-S) [104]; and clinician-rated functional improvement (Clinical Global Impression Scale- Improvement; CGI-I) [104].

Vital signs and reports of adverse events will be monitored at each study visit (Baseline, Week 4, Week 8, Week 12, Week 16) for tolerability and safety monitoring. A phone call with the subject's caregiver at Week 2 of the treatment phase will also be used to monitor for early adverse events. Physical exam and phlebotomy for routine laboratories (Complete Blood Count (CBC); Comprehensive Metabolic Panel (CMP); Liver Function Tests (LFTs), and Thyroid Stimulating Hormone (TSH)) will be conducted at Baseline and Week 12 for the purposes of safety monitoring. Fecal samples will be collected at home in the 48 hr prior to Baseline and Week 12 visits for microbiota analyses.

Schematic Diagram of Study Events:

¹ Behavioral outcome measures (SRS-2, ABC, CGI, RBSR)

²Adverse Events Review

³ Blood chemistries (Comprehensive Metabolic Panel, Liver Function Tests, Thyroid Stimulating Hormone)

Primary Study Endpoints

The primary study endpoint will be percent change in mean SRS-2 total scores from Baseline to Week 12, the end of the active treatment phase.

Secondary Study Endpoints

- Percent change in mean SRS-2 total scores from Week 12 (the end of the active treatment phase) to Week 16 (the end of the discontinuation phase)
- Percent change in mean SRS-2 subscale scores (Social Awareness, Social Cognition, Social Communication, Social Motivation, and Restricted Interests/ Repetitive Behaviors) from Baseline to Week 12 and from Week 12 (the end of the active treatment phase) to Week 16 (the end of the discontinuation phase)
- Change in mean CGI-Severity score from Baseline to Week 12 and from Week 12 (the end of the active treatment phase) to Week 16 (the end of the discontinuation phase)
- Proportion of participants with CGI-Improvement (CGI-I) scores of 1 (very much improved) or 2 (much improved) in each treatment arm at Weeks 12 and Week 16
- Percent change in mean RBSR total scores from Baseline to Week 12 and from Week 12 (the end of the active treatment phase) to Week 16 (the end of the discontinuation phase).
- Percent change in mean ABC subscale scores (Social Withdrawal, Hyperactivity, Inappropriate Speech, Stereotypy, and Irritability) from Baseline to Week 12 and from Week 12 (the end of the active treatment phase) to Week 16 (the end of the discontinuation phase)
- Proportion of participants in each treatment arm meeting responder status, as defined by 10 point or greater reduction in SRS-2 total score AND CGI-I score of 1 (very much improved) or 2 (much improved).
- Proportion of participants in each group meeting partial responder status, as defined by 10 point or greater reduction in SRS-2 total score AND CGI-I score of 3 (minimally improved).

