Sulforaphane (SF), derived from freeze-dried broccoli sprouts, was recently investigated as a treatment for symptoms of ASD in a randomized, double-blind, placebo-controlled trial of 45 male adolescents and young adults (ages 13-30 years old) with moderate to severe autism (clinical trials identifier NCT01474993) [48]. Fifteen participants were randomized to placebo and 29 to SF: each group was treated for 18 weeks, followed by a 4-week discontinuation period and final follow-up at 22 weeks. Forty participants (14 on placebo, 26 on SF) completed the trial; of those participants, 32 (80%) had a reported history of behavioral improvement during fever episodes. The primary outcome was change in symptoms of autism as measured by change in Social Responsiveness Scale (SRS) total scores; additional measures of interest included change in caregiver-completed Aberrant Behavior Checklist (ABC) scores and clinician-rated Autism Clinical Impressions Severity and Improvement Scales (OACIS-Severity and OACIS-Improvement). SRS scores improved significantly more in the SF group compared with the placebo group (-15 units vs -3 units; p=0.02). Considering the 4 non-completers as non-responders, 31% (9/29) SF participants vs 0% placebo participants demonstrated a 25% decrease in total SRS score from baseline (p=0.018). SF participants also demonstrated significantly greater improvement in ABC total and OACIS-Improvement scores, particularly in the domains of social interaction (p=0.003), aberrant/ abnormal behavior (p=0.007), repetitive/ stereotypical behavior (p=0.08), and verbal communication (p=0.008). SF was well-tolerated with no serious adverse events. Two subjects

with a history of seizures had single unprovoked seizures during the course of the study (one after 3 weeks on SF, one 3 weeks after discontinuing SF), and the possibility of seizure as potentially associated with SF could not be ruled out.

Based on available data from Phase I human clinical trials of SF-rich compounds, SF appears to be extremely well-tolerated with minimal risk aside from mild gastrointestinal symptoms, which may include bloating, nausea, and loose stools.

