7.1 Sample Size Determination

We calculated power for comparing groups on change in SRS-2 total score (the primary outcome measure), using a standard approach for linear mixed models (Littell RC, Milliken GA, Stroup WW, Wolfinger RD, Schabenberger O. *SAS for mixed models [electronic resource]*. Cary, N.C.: SAS Institute, Inc.; 2006). We assumed that the mean differences observed in the trial by Singh et al. represented the true values (i.e., we assumed mean differences of 7, 20, 18.4, and 0.4 at weeks 4, 8, 12 and 16, respectively), and we assumed a constant standard deviation of 20, consistent with that observed by Singh et al. Furthermore, we assume within-participants across time correlation of 0.5 (a conservative value) and we assume no more than 15% loss distributed over the 16 weeks of follow-up. Under these assumptions, randomizing 27 participants to each group will provide at least 80% power for an overall test comparing groups across all time points using a two-sided 4 degree of freedom test at the 0.05 significance level.

For the exploratory microbiota analysis, we aim to include a subset of 30 subjects in the sample. In a recent randomized cross-over trial of the effects of broccoli consumption on microbiota composition in 18 healthy adults [Kaczmarek 2017*], participants consuming broccoli exhibited an increase in the ratio of Baceteroidetes to Firmicutes by 37% from baseline to end, compared to a 5% reduction during the control period (p=0.02). With 15 participants per group, we will have >80% power to detect a similar change in the ratio of Bacteroidetes to Firmicutes.

* Kaczmarek JL, et al. Broccoli consumption impacts the human gastrointestinal microbiota. The FASEB Journal, 2017. 31(1 suppl): p.965.

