7.2 Statistical Methods

General linear mixed models (GLMM) will be used to test the primary and secondary hypotheses in longitudinal analyses:

Primary Hypotheses

Compared to control participants, treated participants will show larger changes over time on SRS-2 total scores from Baseline to Week 12, and differences will not be maintained after treatment discontinuation at Week 12 through the end of the follow-up period at Week 16.

GLMM analyses will describe individual patterns of change over time on the SRS-2 Total score. Individual intercepts and slopes will be estimated as random-effects variables, and will be allowed to correlate. The SRS-2 scores from Baseline, Week 4, 8, 12, and 16 will be modeled as a function of treatment, time, time x treatment and will include covariates of age-stratum and the SRS-2 total score from screening. In addition to time, we will add a time-varying variable representing treatment phase (0=treatment, 1=follow-up period) and we cross this variable with treatment, time, and treatment x time. Time will be centered at Week 12. Of interest will be the main effect of treatment (i.e., treatment impact at end of active treatment), treatment x time (i.e., treatment impact on change over time during the active treatment phase), and treatment x time x treatment phase (i.e., treatment differences in change over time during follow-up period). We will use an unstructured covariance matrix. We will first test for any differences between groups across all four groups using a 4 degree of freedom linear contrast of the model parameters. If this overall test is significant at the 5% level, we will then test for differences separately at each time point. We will also report estimated mean differences along with 95% confidence intervals.

Secondary Hypotheses

Compared to control participants, treated participates will show larger changes over time on CGI Severity and RBSR scores from Baseline to Week 12 and will show reduction in those gains after discontinuation through the end of the follow-up period at Week 16.

Compared to control participants, treated participates will show larger changes over time on subscales when treatment impacts were observed on the total scores on the SRS-2, CGI Severity, and RBSR from Baseline to Week 12 and will show reduction in those gains after discontinuation through the end of the follow-up period at Week 16.

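### Week 12 to Week 16 percent-change endpoints for the SRS-2, RBSR and ABC divide by a Week 12 mean that treatment may already have lowered, so losses after stopping are not comparable with gains or between arms

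*Combined protocol and SAP*

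**What the plan says.** The primary endpoint in section 3.1 is "percent change in mean SRS-2 total scores from Baseline to Week 12". The Secondary Study Endpoints list in the same section adds "Percent change in mean SRS-2 total scores from Week 12 (the end of the active treatment phase) to Week 16" and uses the same two-phase form for the SRS-2 subscales, for the RBSR ("Percent change in mean RBSR total scores from Baseline to Week 12 and from Week 12 (the end of the active treatment phase") and for the ABC ("Percent change in mean ABC subscale scores (Social Withdrawal, Hyperactivity, Inappropriate Speech, Stereotypy, and Irritability) from Baseline to Week 12", followed by Week 12 to Week 16). The denominator is not spelled out, but a percent change from Week 12 ordinarily means a percent of the Week 12 mean.

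The two CGI measures are defined differently. CGI-Severity is an absolute change ("Change in mean CGI-Severity score from Baseline to Week 12 and from Week 12") and CGI-Improvement is a proportion.

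Section 7.2 models SRS-2 total scores in points and addresses the off-treatment period with a treatment by time by phase term. Similar models are planned for CGI-Severity and RBSR, and for subscales only if the total shows an effect. Its secondary hypotheses say that treated participants "will show reduction in those gains after discontinuation through the end of the follow-up period at Week 16". The ABC is not named in section 7.2, and no analysis of the percent endpoints is described.

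**The concern.** Asking how much of a gain is lost after stopping requires gain and loss to be on one scale. Here the gain is a percent of the Baseline mean, which randomisation makes similar in the two arms. The loss is a percent of the Week 12 mean, which is measured after randomisation and is the quantity treatment is meant to lower.

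Two things follow whenever the drug works. Within the active arm, a complete return to Baseline is reported as a percent loss exceeding the percent gain, which a reader could take for rebound worsening. Between arms, an identical point change after Week 12 is reported as a larger percent on active. If both arms drift upward once tablets stop, the table shows an arm difference in the direction of the hypothesis. If both drift downward, the active arm appears to improve more, against the hypothesis.

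**Working it through.** **Inputs from the documents.** Section 7.1: "we assumed mean differences of 7, 20, 18.4, and 0.4 at weeks 4, 8, 12 and 16, respectively", SD 20, within-participant correlation 0.5, 27 per arm. Clinical Data to Date, on the earlier trial of sulforaphane in ASD: "SRS scores improved significantly more in the SF group compared with the placebo group (-15 units vs -3 units; p=0.02".

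**Assumed.** The documents give no Baseline SRS-2 mean, so I take B = 90 to 120. The section 7.1 figures are between-arm differences, so turning them into an active-arm path needs an assumed placebo mean that stays flat at B.

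**The plan's own figure.** The documents state no figure for percent change. The stated power of at least 80% for the 4-df test is met as a lower bound. With lambda = (n/2) d'V⁻¹d = 24.85 at n = 27, power is 98% (F) to 99% (chi-square), or 95% to 97% with 15% missing at every visit. That calculation is in points, so the percent denominators do not enter it.

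**Step 1: full return, any Baseline.** With gain D:

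- gain = D/B
- loss on full return = D/(B − D)
- loss ÷ gain = B/(B − D), which exceeds 1 whenever B > D > 0.

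**Step 2: the section 7.1 differences.** The active arm falls 18.4 points by Week 12 and regains 18.4 − 0.4 = 18.0 by Week 16. The true share of the gain lost is 18.0/18.4 = 97.8%. As the endpoints are written, gain = 18.4/B and loss = 18.0/(B − 18.4). The last column is a 10-point rise after Week 12 in both arms: 10/(B − 18.4) on active and 10/B on placebo.

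| B | Week 12 mean, active | Gain | Loss | Loss ÷ gain | 10-point rise: active vs placebo |
|---|---|---|---|---|---|
| 90 | 71.6 | −20.4% | +25.1% | 1.23 | 14.0% vs 11.1% |
| 100 | 81.6 | −18.4% | +22.1% | 1.20 | 12.3% vs 10.0% |
| 110 | 91.6 | −16.7% | +19.7% | 1.17 | 10.9% vs 9.1% |
| 120 | 101.6 | −15.3% | +17.7% | 1.16 | 9.8% vs 8.3% |

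At B = 100, adding the two percentages gives +3.7%, an apparent net worsening, although 0.4 points of benefit remain.

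**Step 3: partial return.** The reported loss equals the reported gain once a fraction 1 − D/B of the gain has gone. At B = 100 that is 1 − 0.184 = 0.816, so losing 82% of the gain already reads as losing all of it.

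**Step 4: the earlier trial's within-arm changes.** With −15 on active and −3 on placebo at B = 100, a 10-point rise reads 10/85 = 11.8% against 10/97 = 10.3%. The effect is smaller and in the same direction.

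**Step 5: a common denominator.** Dividing both phases by B = 100 gives −18.4% then +18.0%, which recovers 97.8%. A 10-point rise reads 10.0% in both arms.

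**The case against.** The strongest reply is that section 7.2 already answers the off-treatment question in points, with estimated differences and 95% confidence intervals, and that no test of the percent endpoints is planned. This stands for SRS-2 total and RBSR. A reader might infer that the discontinuation test or the power is biased; the documents do not support that. The reply is incomplete for the SRS-2 subscales, which are modelled only if the total shows an effect, and it does not cover the ABC. For the ABC subscales, the percent on the Week 12 mean is the only off-treatment summary stated.

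The artefact is also modest for SRS-2 total. With SD 20 and correlation 0.5, the SD of the Week 12 to Week 16 change is 20, so the between-arm standard error is 20 × √(2/27) = 5.4 points. At B = 100 that is 5.4 percentage points, against an artefact of 2.3 for a 10-point shift. This stands, and it makes the SRS-2 problem one of description.

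Other stronger readings also fail:

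- **Every discontinuation endpoint is affected.** CGI-Severity and CGI-Improvement are not.
- **The plan's figures show the active arm returning to its own Baseline.** They are between-arm differences; 0.4 at Week 16 could also arise from improvement on placebo.
- **The rule always favours the drug hypothesis.** Only a shared upward drift does so.
- **Participants scoring zero have no value, or low scorers dominate.** The endpoints are percent changes in mean scores, so a ratio of group means is the natural reading and neither problem arises.

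**Conclusion.** The point holds for the Week 12 to Week 16 endpoints of SRS-2 total, SRS-2 subscales, RBSR total and ABC subscales. On the ordinary reading of the denominator, the direction is certain for any Baseline mean above the gain. The sizes are illustrations that rest on an assumed Baseline and a flat placebo mean: a loss reading as 116% to 123% of the gain where the truth is 97.8%, and equal point changes reading 18% to 26% larger on active (B/(B − 18.4) at B = 120 and 90).

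The consequence is misleading secondary reporting and possible disagreement between the endpoint table and the section 7.2 model. It should be corrected because the remedy is specific and cheap, with the clearest benefit for the ABC.

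**What to change.** In section 3.1, define the Week 12 to Week 16 endpoints for SRS-2 total and subscales, RBSR total and ABC subscales as change in points. Report each as the between-arm difference in Week 16 minus Week 12, with its 95% confidence interval, from the section 7.2 mixed model on raw scores. Name the ABC subscales in section 7.2 and extend that model to them.

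If a percent is still wanted for display, divide the mean change in both phases by the same Baseline mean pooled over the two arms. Gain and loss then share a scale, and the denominator is the same in each arm.

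The cost is revised endpoint wording and tables and one added model for the ABC subscales. No new data are needed. The percent on the Week 12 value is no longer shown.
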